Aim 1: The study population will consist of 200 patients (100 control, 100 treated with Ketorolac) that are admitted to the inpatient surgical service at our level I trauma centers for management of orthopedic trauma care. All trauma patients that are between the ages of 18-75 and with NISS > 9 (moderate injury) [33, 34] will be enrolled and treated according to the standard Advance Trauma Life Support (ATLS) protocol. 100 patients in the control group will receive placebo intravenous saline every 6 hours for their initial 5 days of hospitalization and no NSAID administration. 100 patients randomized to the treatment group will receive 15 mg of Ketorolac every 6 hours for their initial 5 days of hospitalization. A daily blood sample (10 cc) will be collected on Days 1–5 by blinded health care personnel. These blood samples will be analyzed via sandwich ELISA method for concentrations of IL-1, IL-6, IL-10, and PGE2. Serum concentrations will be compared between the treatment and control groups using two-tailed independent t-tests. In addition to the standard trauma labs, patient demographics, injury data (gender, age, BMI, mechanism of injury, NISS, and types of surgical/procedural interventions), injury outcomes (incidence of bacterial pneumonia, ARDS, SIRS, MODS), complications defined in the National Trauma Dataset, and inflammatory data will be compiled, tracked, and maintained in our clinical database (REDCap). Outcome variables (hospital and ICU length of stay and occurrence of pneumonia and/or ARDS and/or SIRS or death), and the predictor variables of interest (inflammatory markers and NISS) will be compared using Poisson regression. The odds of developing post traumatic complications in the different predictor groups will be determined using multiple logistic regressions. The covariates will be adjusted for in the regression models: age, sex, injury severity, severity of head and/or extremity injury, injury mechanism, and injury outcome.

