Aim 2: The enrolled patients will be followed daily by our trained clinical research coordinator. Patient's subjective pain scores will be assessed and documented by the trained nursing staff using Visual Analogue Scale (VAS) daily. Morphine milligram equivalent (MME) along with other pain medication intake will be recorded per day for the duration of Ketorolac or placebo therapy. Patient's clinical course will be monitored closely and daily to ensure no NSAIDs will be administered to the control cohort to ensure consistency and protocol adherence of the study. Once patients are discharged from the hospital, outpatient pain scores will be assessed during routine clinic follow up visits using Patient-Reported Outcomes Measurement Information System (PROMIS) surveys. Opioid and pain modulating medication prescription refills will be monitored using the State All Scheduled Prescription Electronic Reporting system. Patient narcotic requirement will be assessed during all of the routine follow up visits by the same research coordinator in order to maintain consistency. Patients' inpatient and outpatient subjective pain score and MME intake will be compared between the control and treatment groups using two-tailed independent t-tests.

Aim 3:

Finally, analysis will be performed to evaluate the treatment effects between two groups using fracture unions as a dependent variable. The rate of fracture unions will be calculated at 3 month, 6 month and 12 month. Fractures will be considered united if they met the criteria for clinical or radiological union. The baseline clinical factors that are independently associated with fracture unions will be assessed from candidate variables and are entered using a forward ($p<0.05$) and backwards ($p<0.10$) stepwise selection procedure. Finally, the multivariate model will be performed to assess the association of clinical factors with fracture unions starting at 3 month between two groups.

Attachments

Data Collection & Research Materials

In this section, please provide the following:

- Describe all sources or methods for obtaining research materials about or from living individuals (such as specimens, records, surveys, interviews, participant observation, etc.), and explain why this information is needed to conduct the study.
- For each source or method described, please list or attach all data to be collected (such as genetic information, interview scripts, survey tools, data collection forms for existing data, etc.).

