Monitoring of the progress of clinical investigations and the safety of participants: The proposed medication for this investigation is a commonly utilized substance for pain control. Patients will be monitored for adverse effects of these medications continuously while they are an inpatient. Please refer to Study Drug information and Informed Consent Appendix B for further details. The research team will work closely with the medical management team daily to note if any of these difficulties should arise. Other minor side effects will be recorded and monitored through chart review (nausea, abdominal pain, minor bruising and bleeding) at the conclusion of the inpatient admission. If necessary, blinding will be broken if any potential side effects are noted and the information regarding treatment would be helpful to the treating team. The clinical medical monitor of the investigation will be obtained with the help of CCTS and that person will be added to the study personnel. The PI will be blinded to the subject treatment arm, and thus limit bias in reporting.

Compliance:

The research team will meet monthly to discuss and review any of the above recorded events and report adverse events to the IRB accordingly. A yearly report will be filed with the IRB with regards to overall data safety. Study suspension/termination: In the event that there is a noted increase in the serious side effects of taking the study drug, the study will be suspended for review.

Data Accuracy:

The research team will meet monthly to go over the collected data and perform spot reviews to determine the accuracy of the data collection from the medical record and study procedures.

[Back to Top](#)

Future Use and Sharing of Material (e.g., Data/Specimens/Information)

If the material collected for this study will be used by members of the research team or shared with other researchers for future studies, please address the following:

- list the biological specimens and/or information that will be kept
- briefly describe the types, categories and/or purposes of the future research
- describe any risks of the additional use
- describe privacy/confidentiality protections that will be put into place
- describe the period of time specimens/information may be used
- describe procedures for sharing specimens/information with secondary researchers
- describe the process for, and limitations to, withdrawal of specimens/data

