Interventional Model Description: Compare the effectiveness of a NSAID to placebo in acute trauma setting.

Masking: Triple (Participant, Care Provider, Investigator)

Masking Description: Participant medical team will be blinded to the treatment or placebo intervention.

3. Outcome Measures

Primary Outcome: Length of Hospital Stay

Secondary Outcomes:

- Daily Concentrations of IL-1, IL-6, IL-10, and PGE2
- Incidence of Post-Traumatic Complications (e.g., bacterial pneumonia, SIRS, MODS, ARDS, and AKI)
- Mortality
- Visual Analogue Pain Scores
- Inpatient Morphine Milligram Equivalents
- Change in Inpatient Subjective Pain Reports
- Change in Outpatient Subjective Pain Reports

4. Background

Accidental trauma is the 4th leading cause of death in the United States, and it is associated with a complex inflammatory response. This response is associated with post-traumatic complications such as multi-organ dysfunction syndrome (MODS), bacterial pneumonia, acute respiratory distress syndrome (ARDS), systemic inflammatory response syndrome (SIRS), and post traumatic pain (PTP). It is unknown whether early modulation of inflammatory cytokines is associated with improved patient outcomes, reduced narcotic requirements, and improved patient subjective pain after hospital discharge.

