Enrolled patients will be monitored daily by research staff throughout their hospital stay and routine outpatient clinic visits. Patient's subjective pain scores will be assessed and documented by the trained nursing staff using Visual Analogue Scale (VAS) daily. Pre-injury narcotics use along with other pain modulating medication intake will be recorded per day in morphine milligram equivalent (MME) for the duration of ketorolac or placebo therapy in our password protected database. Patients' clinical course will be monitored closely and daily by research staff to ensure no NSAIDs will be administered to the control cohort to ensure consistency and protocol adherence. After patient discharge, various patient surveys will be used to assess patient pain, function, and quality of life. Opioid and pain modulating medication prescription refills will be monitored using State Scheduled Prescription Electronic Reporting System. Patient narcotic requirement will be assessed during all the routine follow up visits by the same research staff to maintain consistency.

11. Data and Specimen Banking

Blood sample specimens obtained from the research subjects will be labeled with the patient's unique study ID number and will be stored in the CCTS lab until analysis. Following analysis, the specimens will be disposed of in accordance with UK policies. No specimens will be retained for future studies. The stored de-identified data from the study will be kept for a minimum of 6 years for records in the event follow-up studies are pursued and will remain protected and encrypted. Data will be permanently

deleted following this time period. The banked data will be stored on a password-protected research drive. Upon conclusion of the study, the data will be stored in a password encrypted file that only the PI has access to.

12. Data Management

Following initial enrollment, each patient will be assigned a unique patient identifier. All electronic documentation containing total morphine equivalents, specimen results, and all other medical information will be associated with this unique patient identifier during analysis. All protected health information will be stored in a separate, password-protected research file that will not be accessed regularly. Following our secondary analysis, all personal health information will be removed from our electronic files and destroyed in accordance with patient privacy guidelines.

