Data obtained at the UK during the study will be recorded and stored using password protected spreadsheet on the department's secure drive and will be maintained at the hospital by the research staff. Final analysis will be conducted using Excel spreadsheets. All documents will be stored on a password-protected research drive and only research personnel will have access to its content. Paper documents, including consent forms, will be stored in a locked cabinet in a secure research room in the Kentucky Clinic Suite K434.

All study personnel have completed human subject protection, responsible conduct of research, and patient confidentiality training. Only IRB-approved research personnel will administer consents and perform phone surveys. All efforts will be made to maintain the confidentiality of the patient reported data. Only study personnel listed in eIRB will have access to identified study data.

13. Provisions to Monitor the Data to Ensure the Safety of Subjects

Subjects in this study will be exposed to greater than minimal risk but presenting the prospect of direct benefit to individual in the study. The patients will be monitored continuously as inpatients post-operatively and any issues with medication effects, wound healing, or other medical complications will be logged as adverse events. Blinding will only be broken for unexpected complications potentially relating to ketorolac administration and the research study. The research team will meet monthly to monitor data collection and handling. During this time, study staff will also review adverse events logs.

14. Withdrawal of Subjects

We do not anticipate any situation in which a subject would be withdrawn from the study by the researchers should they wish to remain. We anticipate analyzing the data via an intention to treat analysis and thus would include data from all subjects initially enrolled, even if they developed an intolerance or medical contraindication to continuing the study.

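### The NSAID restriction names only the control arm of a masked trial; one rule for both arms, with no further ketorolac after the study course, would fit the masking and cover the ketorolac arm

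*Combined protocol and SAP*

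**What the plan says.** Three sentences restrict non-study NSAIDs, and each names controls only.

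- Protocol section 10(e): each patient's "clinical course will be monitored closely and daily by research staff to ensure no NSAIDs will be administered to the control cohort". No end date is given.
- IRB application, Research Procedures, Aim 2: the course is "monitored closely and daily to ensure no NSAIDs will be administered to the control cohort". Again no end date.
- IRB application, Research Procedures, Aim 1: controls receive "placebo intravenous saline every 6 hours for their initial 5 days of hospitalization and no NSAID administration". The parallel sentence for the other arm, "100 patients randomized to the treatment group will receive 15 mg of Ketorolac every 6 hours for their initial 5 days of hospitalization", carries no such limit.

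On masking, protocol section 2 (Study Design) covers participant, care provider and investigator, and adds: "Participant medical team will be blinded to the treatment or placebo intervention". The IRB application (Data and Safety Monitoring) says that the PI is blinded. Unblinding is tied to events. Section 13 of the protocol says "Blinding will only be broken for unexpected complications potentially relating to ketorolac administration and the research study", and the IRB application says "If necessary, blinding will be broken if any potential side effects are noted".

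On ketorolac itself, section 10(d) gives 15 mg every 6 hours for 5 days. Section 28 gives the labeled duration as up to 5 days in adults. Sections 10(d), 15, 25 and 28 describe ketorolac as part of the site's usual acute trauma pain protocol. Section 28 also leaves additional treatment to the attending surgeon, independently of the study.

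**The concern.** A rule that depends on the arm can be applied as written only by someone who knows the arm. The clinicians who order analgesia do not. The rule also faces one way: it keeps NSAIDs away from controls, but says nothing about a second NSAID on top of study ketorolac, or about routine ketorolac once the study course ends.

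Two things are at stake. One is participant safety in the ketorolac arm. The plan treats renal and bleeding risk as relevant: section 5 excludes chronic renal disease, active GI bleeding and coagulation defects, and section 3 lists AKI among the complications. The other is the blind, because enforcing a control-only rule tells the treating team which arm the patient is in.

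**Working it through.** The plan gives no figure on this point to reproduce. The check sets the sentences side by side, with a little arithmetic for scale.

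**Who the rule names.** Planned enrollment is 56 per arm, 112 in total (protocol sections 6 and 10(b)). Named by the rule: 56/112 = 50%. The IRB application's 100 of 200 gives the same 50%. Ketorolac-arm participants named: 0 of 56.

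**Study exposure (section 10(d)).** 15 mg × 4 per day = 60 mg per day. Over 5 days that is 4 × 5 = 20 doses, and 20 × 15 mg = 300 mg.

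**Labeled days left (section 28).** 5 − 5 = 0. One further day of ketorolac makes 6 days, and 6/5 = 1.2 times the labeled duration. Section 5 requires an anticipated admission of at least 5 days, so inpatient time after the last study dose is plausible. The plan does not say how many patients would have it.

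**What happens under each way of working:**

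| Who applies the rule | Days 1–5 | After Day 5 | Effect on the blind |
|---|---|---|---|
| Masked clinicians, who withhold NSAIDs from everyone | Ketorolac arm protected as a by-product | Protected if the rule is open-ended (10(e), Aim 2); not protected if it ends with the initial 5 days (Aim 1) | None |
| Staff who know the arm, enforcing it for controls only | Ketorolac arm not protected | Ketorolac arm not protected | Each intervention identifies a control |

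The first row is the sensible course, but no sentence instructs it. The second row is the literal reading, and it fails on both counts. The documents do not settle which applies. The rule is assigned to research staff, whose masking is not stated. The PI is blinded, and section 20 has the orthopedic PI acting as research coordinator, but the personnel list shows several other coordinators.

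**Search for a limit elsewhere.** The IRB form asks for forbidden and permitted medications, and the Research Procedures answer has no such list. Section 28 describes the label but gives no instruction about ketorolac ordered outside the study. Section 20 says that the surgical team is counseled about the study and its role, without mentioning NSAIDs.

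**The case against.** The strongest reply is that a masked prescriber cannot order any NSAID without risking one for a control. Obeying the rule therefore already protects everyone, and a duplicate NSAID needs someone to ignore it. For masked prescribers on Days 1–5 this stands. A reader might infer that the rule is impossible to follow, and the text does not support that. What remains is that the working rule differs from the written one, and that after Day 5 the protection depends on which of two wordings governs.

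Second, attachments that were not supplied are natural places for such limits: the study drug forms and prescribing information, the consent appendix on drug effects, and the adverse event risk mitigation plan. This also stands. The point is confined to the supplied text.

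Third, there are safeguards: daily recording of pain medication during therapy, daily compliance checks, creatinine and BUN among the labs, adverse event monitoring, and suspension if serious side effects increase. These would help to detect a problem. None tells a clinician not to order a second NSAID, and the recording rule for pain medication covers only the duration of study therapy.

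Fourth, AKI is listed as a complication of trauma, not as a ketorolac effect, and no supplied sentence quantifies harm from a duplicate NSAID. That is correct, so no harm estimate is offered.

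Fifth, the IRB comments of August 2023 record the study as closed to enrollment, with 108 enrolled in the continuation review. New dosing rules would reach no new participants. The point therefore concerns the plan as written and any reuse of it.

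A reader might also infer that NSAID use diluted the treatment contrast and cost power. The documents do not support this: NSAIDs in controls are what the plan does bar, and no rate of NSAID use is given.

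**Conclusion.** The concern holds in a limited form. In the supplied text the NSAID restriction is specific to one arm of a trial that masks those who would order the drugs. Masked clinicians can comply only by an unstated extension to everyone. Staff who know the arm would disclose it by complying, and the rule would leave the ketorolac arm without protection.

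Its size is structural: the rule names none of the 56 planned ketorolac patients, and 0 labeled days remain after the study course. The number who would receive a duplicate or late NSAID cannot be derived. The 1.2 ratio is one extra day restated; it does not measure harm.

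This rests on two assumptions: that the attachments contain no limit for both arms, and that routine ketorolac remains available to enrolled patients, as the protocol's description of usual care suggests. It should be read as a low-cost safety and masking correction. It is not evidence that anyone was harmed or unblinded, and it does not bear on the sample size, the intention-to-treat analysis or the efficacy results.

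**What to change.** 1. In protocol section 10(e) and IRB application Aim 2, replace the control-only clause with: *no participant in either arm receives a non-study NSAID during the 5-day study-drug period*. Add the same limit to the treatment-group sentence of Aim 1. The term non-study keeps study ketorolac allowed.
2. After the last study dose, treat every participant still masked as having used the 5 labeled days, and give no further ketorolac in that admission. Do not unblind for this purpose alone.
3. Delete the control-only wording; do not carry it past Day 5. This leaves other NSAIDs after Day 5 to usual care in both arms. If a longer limit is wanted, it should apply to both arms alike.
4. State items 1 and 2 in the surgical-team counseling of section 20.
5. Check the attachments first. If one already contains such a limit, bring these sentences into line with it.

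The cost is protocol wording and a line in the counseling, with no extra patients, visits or analyses. The real downside is that placebo patients lose routine ketorolac after Day 5 if the present rule ends then. If the present rule is open-ended, they have lost it already.

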		Day 1	Day 2	Day 3	Day 4	Day 5	Discharge	2 Week	6 Week	3 Month	6 Month	12 Month
Inclusion/Exclusion Review	X											
Informed Consent	X											
Blood Sample		X	X	X	X	X						
Ketorolac Intervention		X	X	X	X	X						
MME		X	X	X	X	X	X					
VAS		X	X	X	X	X	X	X	X	X	X	X
Post-Traumatic Complications		X	X	X	X	X	X	X	X	X	X	X

10. Procedures Involved

- Patient identification:** Patients will be identified on morning intake rounds by the trauma team and the research staff who are present daily to screen and enroll patients.
- Screening/Enrollment:** Study population will consist of 112 patients (56 control, 56 treatment) admitted to the inpatient surgical service at University of Kentucky (UK) level I trauma center for management of trauma care. Trauma patients that are between the ages of 18-75 and with NISS > 9 (moderate injury) with anticipated admission of ≥ 5 days (to ensure completion of the treatment) will be enrolled (Grisoni et al., 2001; Stevenson, Segui-Gomez, Lescohier, Di Scala, & McDonald-Smith, 2001). All patients will be initially treated according to the standard Advance Trauma Life Support (ATLS) protocol and standard ICU protocols (if applicable). Experienced clinical research staff will prospectively identify patients who meet the inclusion criteria and none of the exclusion criteria detailed in table 2.
- Randomization:** Consented patients will be randomized using a computer-generated algorithm to the control group (1-2 mL of intravenous saline every 6 hours for 5 days after admission) or treatment group (15 mg of intravenous ketorolac every 6 hours for 5 days after admission).
- Treatment:** Ketorolac (15 mg) has been chosen as the treatment of choice for several reasons:
 - Ketorolac has a similar pharmacodynamics profile as indomethacin, which was used

in our previous animal model (Xiang et al., 2012).

(2) It is readily available intravenously obviating limitations of oral intake.

(3) In numerous prospective clinical studies, ketorolac infusion produced no change in cardiac or hemodynamic parameters in patients undergoing major vascular surgery (Camu, Van Overberge, Bullingham, & Lloyd, 1990; Peirce, Fragen, & Pemberton, 1990).

(4) 30 mg is the approved dose that is consistent with United States Food and Drug Administration (FDA) labeling per the package

(5) Ketorolac is part of the routine trauma acute pain protocol

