Patients with pre-existing medical co-morbidities and contraindications to ketorolac will be excluded from the study (see 5 for detailed exclusion criteria)

Patients in the treatment group will receive 15 mg IV ketorolac every 6 hours for 5 days after admission.

e. **Post-operative inpatient care:** Enrolled patients will have daily blood samples (10 cc) will be collected post-admission and at 24 hours intervals for 5 days by blinded health care personnel. The initial blood sample will be collected within 12 hours of initial injury and before the first scheduled administration of ketorolac to establish baseline cytokine profile. Subsequent blood sample collection will be 24 hours apart. Medication compliance and monitoring will be performed daily by the same research coordinators.

Sandwich ELISA will be used to determine the concentrations of IL-1, IL-6, IL-10, and PGE2 in obtained blood samples. Blinded quality control samples will be included in every batch for each ELISA assay. This will allow for the calculation of coefficient of variation (CV) within and across patient cohorts. In the present study, the CV will be calculated for IL-1, IL-6, IL-10, and PGE2. If wide variations are observed among the analytes during the analysis, we will restrict our analysis to analytes in which the CV is less than 20%.

In addition to the standard trauma labs (Sodium, Potassium, Creatinine, Lactic acid, Glucose, Platelet, blood urea nitrogen (BUN), hematocrit, and white blood cell count), patient demographics (sex, age, and BMI), injury data (mechanism of injury, NISS, and types of surgical/procedural interventions), posttraumatic complications (occurrence of bacterial pneumonia, ARDS, SIRS, MODS), complications defined in the National Trauma Dataset, and inflammatory data will be collected. This data will be maintained in our clinical database (REDCap) by a full-time Clinical Study Coordinator.

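### As worded, the adverse-event log and side-effect review follow the inpatient stay, so observation time for those events depends on length of stay, the primary outcome

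*Combined protocol and SAP*

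**What the plan says.** Two places describe how adverse events are captured. Of these events, protocol section 13 says: "The patients will be monitored continuously as inpatients post-operatively and any issues with medication effects, wound healing, or other medical complications will be logged". The Data and Safety Monitoring part of the E-IRB form says: "Patients will be monitored for adverse effects of these medications continuously while they are an inpatient". It adds a chart review for other minor side effects, whose list and timing read "nausea, abdominal pain, minor bruising and bleeding) at the conclusion of the inpatient admission". Neither text gives a first or last day for recording, and Table 1 (section 9) has no adverse-event row.

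Section 3 gives "Primary Outcome: Length of Hospital Stay". On dosing, section 10d says: "Patients in the treatment group will receive 15 mg IV ketorolac every 6 hours for 5 days after admission". Section 10 enrols patients with an anticipated stay of at least 5 days so that the course can be completed.

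Some collection continues after discharge. The Table 1 row "Post-Traumatic Complications" is marked on Days 1 to 5, at discharge, at 2 and 6 weeks, and at 3, 6 and 12 months. Section 10 also says: "Enrolled patients will be monitored daily by research staff throughout their hospital stay and routine outpatient clinic visits". The SAP (section 7) names no between-arm analysis of adverse events. The interim results pasted into item 7 of the continuation review nevertheless conclude that short-term harms were not apparent on ketorolac.

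**The concern.** For an event that is found only through the inpatient log or the end-of-admission chart review, the time at risk of being recorded equals the length of stay. If ketorolac shortens stay, its patients are watched for less time. With the same daily risk in both arms, the ketorolac arm would then show fewer such events, and the distortion favours ketorolac when the primary outcome is positive. A patient who goes home at day 5 has almost no recorded observation after the last dose. Wound healing, which section 13 names, may show a problem only at a clinic visit.

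No planned test is at stake. The exposure is in descriptive safety statements like the one in the interim results, if they rest on counts from windows of unequal length.

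The two texts also describe the window differently. Section 13 speaks of post-operative monitoring, while the E-IRB text covers the inpatient stay without that limit. Dosing starts at admission, and section 21 says that patients wait in hospital for surgery.

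**Working it through.** **The plan's own figure.** Section 6 gives a difference of 0.928 days, SD 1.5 days, alpha 0.05, 80% power and 42 per group. A two-sided two-sample t-test gives n = 42.0 per group and 80.0% power at 42. Dropout: 84 / (1 − 0.25) = 112, or 56 per group. The figure reproduces, so 0.928 days is used below as the planned difference in stay.

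**Assumptions.** The documents give no mean control stay L, no event rates and no event timing. L is taken as 6 to 15 days. The calculation covers only events seen solely through the inpatient log or review, with no true drug effect on risk.

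**Case 1: constant daily rate to discharge.** The expected count is proportional to days observed, so the relative fall on ketorolac is 0.928 / L.

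- L = 6: 0.928 / 6 = 0.1547
- L = 7: 0.928 / 7 = 0.1326
- L = 10: 0.928 / 10 = 0.0928
- L = 15: 0.928 / 15 = 0.0619

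The range is about 6% to 15%.

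**Case 2: lower rate after day 5.** Let the rate after day 5 be f times the rate in days 1 to 5, with every patient staying at least 5 days. The control count is proportional to 5 + f(L − 5), and the relative fall is 0.928f / [5 + f(L − 5)]. With f = 0.25 the numerator is 0.232.

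- L = 7: 0.232 / 5.50 = 0.042
- L = 10: 0.232 / 6.25 = 0.037
- L = 15: 0.232 / 7.50 = 0.031

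The range is about 3% to 4%.

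**Case 3: all events in days 1 to 5.** Here f = 0, and the fall is 0% provided that every patient stays at least 5 days.

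**Case 1 in patients.** Assume a 20% control risk per stay. The daily hazard is h = −ln(0.8) / L, and the ketorolac risk is 1 − exp[−h(L − 0.928)].

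- Control: 0.20 × 56 = 11.2 patients with an event
- Ketorolac, L = 7: 17.6%, or 9.9 of 56
- Ketorolac, L = 15: 18.9%, or 10.6 of 56

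The gap is 0.6 to 1.3 patients per 56.

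**What collection after discharge covers.** Section 3 lists post-traumatic complications as pneumonia, SIRS, MODS, ARDS and AKI, given as examples. Table 1 follows these on a fixed schedule to 12 months, so the calculation does not apply to them. The minor side effects in the E-IRB text and the wound healing in section 13 are not named there. For the period after discharge, section 10 names pain, function, quality of life, prescription refills and narcotic requirement. No text says whether an event found at a clinic visit enters the adverse-event log.

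**The case against.** A reader might infer that all safety observation ends at discharge. The documents do not support this. The complications row runs to 12 months, section 10 extends monitoring to clinic visits, and no sentence says that logging stops at discharge. This part of the objection stands in full: the point is limited to the log and the side-effect review as worded.

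A reader might also infer that a shorter stay must lower the ketorolac count, or that a planned safety comparison is biased. Neither follows. The first depends on when events occur: the anticipated stay of at least 5 days is meant to cover the treatment course, and the distortion vanishes if events are confined to it. As for the second, section 7 contains no adverse-event comparison. The logistic regression in the E-IRB research procedures concerns complications, which Table 1 follows on a fixed schedule.

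A third tempting reading is that section 13 excludes pre-operative doses and patients who have no operation. Section 10e uses a post-operative heading for care that includes a blood sample taken before the first dose, and the E-IRB text covers the inpatient stay. The wording is loose and needs only to be reconciled.

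Finally, the attachment list names an adverse-event risk mitigation plan, and the E-IRB text refers to study drug information and a consent appendix for detail. None of these is in the documents reviewed, and one of them may define a window.

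These points narrow the concern without removing it. Both visible descriptions of adverse-event capture are tied to the stay, and nothing visible carries the listed side effects past it.

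**Conclusion.** The point holds in limited form. Followed as written, the log and the side-effect review have an observation time that depends on the primary outcome. Ketorolac counts of those events could be lower for that reason alone: by about 6% to 15% at a constant daily rate (control stay 15 down to 6 days), by about 3% to 4% if the rate after day 5 is a quarter of the earlier rate (control stay 7 to 15 days), and by 0% if all events fall in the 5 treatment days and every patient stays that long. These figures rest on the planned 0.928-day difference being real, on assumed stays and event timing, and on events being captured only through the inpatient routes. The named complications are unaffected, and no prespecified test is affected. It is a cheap improvement that would make descriptive safety statements comparable between arms.

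**What to change.** - In section 13 and the E-IRB Data and Safety Monitoring text, record adverse events and the listed side effects from first dose to one fixed day in every patient, whether or not operated on or discharged. Use the existing 2-week visit or chart review, and check wound healing also at the existing 6-week visit. Both visits fall within follow-up whether it ends at 6 weeks (section 9 text) or 12 months (Table 1).
- Add an adverse-event row to Table 1, and say whether events found after discharge enter the log.
- Base any between-arm safety statement on this common window, or report events per patient-day. The fixed window is preferable, because a per-patient-day rate assumes a roughly constant rate. If all events fell in days 1 to 5, a 7-day control stay would make the ketorolac rate look 7 / 6.072 = 1.15 times as high with no true difference.
- Reconcile the post-operative wording in section 13 with the inpatient wording in the E-IRB text.

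The cost is a few sentences, one table row, and a few minutes at existing visits or in chart review. No visit is added. The drawback is that some minor events after discharge will rest on patient recall. The E-IRB comments say that enrolment is closed, so for patients already treated the practical routes are chart review to a fixed day or per-patient-day reporting.
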